## Ethics and approvals

This study complies with the Helsinki declaration. Participation was voluntary and consent could be withdrawn at all times. The protocol will be made available on the website [clinicaltrials.gov](https://clinicaltrials.gov).

## *Data Protection Authority*

Approval for data collection, handling and storage has been granted by the data protection authority for the Capital Region (Region Hovedstaden) with case number P-2023-90. This includes approved data agreements between the Danish Regions, with a designated data manager from each participating hospital.

### *Research Ethics Committee*

The Research Ethics Committee (VEK) and the regional research ethics committee for the Capital Region of Denmark (Region Hovedstaden) have been presented with the project description and protocol and have waived the need approval due to Danish legislation. Case number F-23004686.

### *Informed consent*

Verbal informed consent is obtained during the inclusion process for the cohort study on acute pain after cesarean section ([name] et al. 2023) and a written description of the consent is electronically sent to the patients. The study concludes with a questionnaire after 30 days. In this questionnaire, patients are asked if they wish to continue participating in the survey with questionnaires at 5 weeks, 2, 3, 6, and 12 months after their CD. They provide consent by checking the questionnaire, and then receive a written consent statement with information that participation is voluntary, that their data will be securely stored and a description of how to withdraw consent. In the questionnaires after 12 months, 2, 3, and 4 years, the patients are once again asked about their willingness to continue participating in the survey. If they consent, a new consent statement is sent to them annually. This is approved by the data protection authority for the Capital Region of Denmark (Region Hovedstaden) with case number P-2023-90.

### *Data Processing and statistics*

All data will be handled in the REDCap database. Descriptive statistics will be used to analyze data. Continuous data will be summarized as median (interquartile range) or mean (standard deviation) if the data is normally distributed, and categorical data as frequency (percentage). Subgroup analyses are planned for: Severe acute pain and the association of persistent pain; the association between uterine exteriorization versus in situ repair and the occurrence of persistent pain; as well as the prevalence of chronic pain before pregnancy and its association with the development of persistent pain. We will try to minimize missing data as much as possible by sending questionnaires directly to the participants mobile phones and sending reminders. The amount of missing data will be accounted for when describing data. The sample size is determined by convenience, with an expected participation rate of approximately half of the 700 patients from the initial cohort study agreeing to continue with the questionnaires on persistent pain. We analyze the data when the last of the included patients have completed the 12-month questionnaire and again after every year.

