## Method

### Study design

Prospective Danish multicenter cohort study based on Patient-Reported Outcome Measures (PROM) collected by SMS-based questionnaires and clinical data from electronic health records.

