## Number of participants

We aim to include at least 300 patients from all 5 regions in Denmark. The final number of participants will depend on the cohort size from the ongoing study ([name] et al. 2023).

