#### *Exploratory outcomes*

1. Recall of acute pain at 12 and 24 hours after CD. Asked 12 months after CD.
2. Percentage of patients experiencing pain with an NRS > 3 at 1, 2, 3, and 12 months, as well as 2, 3, 4, and 5 years after CD.
3. Association between severe acute pain (NRS > 6) during the first 24 hours and the occurrence of persistent pain at 6 and 12 months after CD.
4. Prevalence of chronic pain before pregnancy.
5. Prevalence of chronic pain before pregnancy and its association with the development of persistent pain at 6 and 12 months, and 2, 3, 4, 5 years after CD.
6. Association between uterine exteriorization versus in situ repair in CD and the occurrence of persistent pain at 6 and 12 months, as well as 2, 3, 4, and 5 years after CD.

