## Inclusion Period

01.11.2023-30.07.2024, 2-7 months depending on the rate of inclusion at the different sites.

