### *Anesthesia information*

- Spinal anesthesia: Bupivacaine, sufentanil, fentanyl, morphine. Mg and ml.
- Was the patient given an epidural-spinal? Yes/No
- Was general anesthesia administered as the initial preference for the patient? Yes/No
- Was the spinal anesthesia converted to epidural? Yes/No
- Was the spinal anesthesia converted to general anesthesia? Yes/No
- Was the spinal repeated following a failed spinal? Yes/No
- Was it necessary to supplement the spinal anesthesia with opioids, nitrous oxide, or similar due to breakthrough pain during the operation? Yes/No
- Did the patient have an epidural when going to the maternity ward after the recovery period? Yes/No. If yes: When was the epidural discontinued? Date and Time.

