### *Operation information*

- Operation time (minutes)
- Intraoperative bleeding. ml.

- Has the uterus been exteriorized during the operation? Yes/No/The information was not found in the medical record.
- Postoperative bleeding within the first 48 hours requiring blood transfusion. Yes/No
- Reoperation within the first 30 days: Yes/No. If yes: Abdominal bleeding/Vaginal bleeding/Suspected retained tissue or endometritis/Infection at the incision site/other reason

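### The comparison of uterine exteriorization with in situ repair is fixed as purely descriptive in a multicenter, non-randomised cohort, so any hospital differences in both technique and pain would be mixed into the association

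*Protocol*

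**What the plan says.** Exploratory outcome 6 (Protocol, Exploratory outcomes) is the "Association between uterine exteriorization versus in situ repair in CD and the occurrence of persistent pain at 6 and 12 months", continued at 2, 3, 4 and 5 years, which makes six time points. Data Processing and statistics lists the same comparison among the planned subgroup analyses, as "the association between uterine exteriorization versus in situ repair and the occurrence of persistent pain". Its statement of method is "Descriptive statistics will be used to analyze data", with categorical results given as counts and percentages. That section names no stratification, site term or adjustment.

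The study is a prospective multicenter cohort (Study design), so the technique is observed and not assigned. On its spread, Number of participants says: "We aim to include at least 300 patients from all 5 regions in Denmark".

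The exposure comes from the health record and has three possible values (Operation information): "Has the uterus been exteriorized during the operation? Yes/No/The information was not found in the medical record". The planned comparison has two groups, and the protocol does not say where the third value goes. On missing data it says only that questionnaires go straight to patients' phones with reminders, and that the extent of missing data will be taken into account in the description.

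**The concern.** A crude percentage per technique, taken over all patients, is a fair comparison only if the two groups are alike in everything else that affects pain. In a multicenter cohort, hospital is an obvious way for them to differ. If some hospitals exteriorize more often and also have more persistent pain for other reasons, the crude figures show an association that no hospital would show on its own. The reverse pattern could hide a real association.

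The protocol itself collects items of care that may vary between patients, for example "Spinal anesthesia: Bupivacaine, sufentanil, fentanyl, morphine. Mg and ml", nerve blocks and dexamethasone. If these cluster by hospital together with technique, the crude contrast carries them too.

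The stake is moderate. The outcome is exploratory, but it concerns a modifiable surgical step, it is to be reported at several time points, and a reader may take the published association as an effect.

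**Working it through.** **The plan's own figure.** The expected sample is about half of the 700 patients in the parent cohort: 0.5 × 700 = 350. This agrees with the target of at least 300 (300/700 = 43% participation). No figure is given for the exteriorization comparison itself.

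**Assumed inputs (none is in the protocol).** Two equal groups of hospitals, A and B. Persistent pain is 15% in A and 8% in B for reasons unrelated to technique. The share exteriorized is e in A and 1 − e in B. Within each group, technique has no effect.

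**Crude percentages**
- Exteriorized: e × 15% + (1 − e) × 8%
- In situ: (1 − e) × 15% + e × 8%

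| Use in A / B | Exteriorized | In situ | Crude risk ratio |
|---|---|---|---|
| 50% / 50% | 7.5 + 4.0 = 11.5% | 7.5 + 4.0 = 11.5% | 1.00 |
| 70% / 30% | 10.5 + 2.4 = 12.9% | 4.5 + 5.6 = 10.1% | 1.28 |
| 90% / 10% | 13.5 + 0.8 = 14.3% | 1.5 + 7.2 = 8.7% | 1.64 |

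In this set-up the false risk difference is the difference in use times the difference in pain: 0.4 × 7 = 2.8 points and 0.8 × 7 = 5.6 points. It is zero if either factor is zero. If the high-pain hospitals are those that exteriorize less, the 90/10 case reverses to 8.7/14.3 = 0.61.

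**Stratified by hospital group.** The Mantel-Haenszel risk ratio is Σ(a·n₀/N) / Σ(c·n₁/N), where a and c are cases among n₁ exteriorized and n₀ in situ patients. With 175 patients per group and 90/10 use:
- A: a = 0.15 × 157.5 = 23.625 and c = 0.15 × 17.5 = 2.625. Both terms are 2.3625.
- B: a = 0.08 × 17.5 = 1.4 and c = 0.08 × 157.5 = 12.6. Both terms are 1.26.
- Ratio: 3.6225/3.6225 = 1.00.

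**Price in precision.** The Mantel-Haenszel risk difference weights each stratum by w = n₁n₀/N, and its variance here is Σw·p(1 − p)/(Σw)².
- 90/10 use: w = 157.5 × 17.5/175 = 15.75 per group. Variance = 15.75 × (0.1275 + 0.0736)/31.5² = 0.00319, a 95% half-width of 11.1 points. The crude half-width is 6.7 points.
- 70/30 use: w = 122.5 × 52.5/175 = 36.75 per group. Variance = 36.75 × 0.2011/73.5² = 0.00137, a half-width of 7.2 points against 6.7.
- A hospital that uses one technique only has w = 0.

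**Expected cases.** Applying the rates quoted in Background to 350 patients: 5.9% gives 20.65 (about 21), 11% gives 38.5 (about 39) and 27% gives 94.5 (about 95). Those studies may define pain differently from the NRS threshold used here, and full response is assumed, so this is only a range.

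**The case against.** The strongest objection is that the protocol nowhere says hospitals will be pooled, and a statistical analysis plan, which is not shown, could stratify by site. The first part is correct: pooling is inferred from the descriptive method. But the protocol does more than stay silent. It chooses a method, and that method cannot separate technique from hospital.

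Several stronger readings are tempting, and the document does not support them:
- **Technique or anesthesia follows surgeon or departmental habit.** The protocol says nothing on how technique is chosen. The anesthesia and pain-management items are data fields and are no evidence of local protocols.
- **Sites contribute unequal numbers.** The period is given as "2-7 months depending on the rate of inclusion at the different sites". Slower sites may recruit longer to reach similar numbers. The illustration does not need unequal numbers.
- **Departments record only exteriorization, so their in situ repairs become not found.** This is possible but hypothetical. The separate category in fact keeps unknown apart from No.
- **The study will claim an effect of technique.** The wording is association, the outcome is exploratory, and the study's stated aim is descriptive.

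Two practical objections stand in part. With few cases, hospital strata may be sparse and the result inconclusive. Stratifying by hospital also leaves differences between surgeons or patients within a hospital, such as the number of previous cesareans. Both are reasons to report the stratified estimate beside the crude figures and not in their place.

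**Conclusion.** The point holds in conditional form. As written, the protocol yields a crude contrast for a non-randomised exposure in a multicenter cohort. If technique use and persistent pain both differ by hospital, that contrast is confounded by site. On the assumed rates the false risk ratio is 1.28 to 1.64, or below 1 if the pattern runs the other way, and it is 1.00 if either condition fails. The protocol has no site figures, so these numbers show what could happen and do not estimate this study's bias.

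The unplaced third value of the exposure is a smaller gap that the same table of counts would settle. Because the outcome is exploratory and worded as an association, this is a worthwhile improvement to the analysis and does not threaten the primary outcome.

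**What to change.** In Data Processing and statistics, keep the crude percentages and add wording such as:

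*For exteriorization versus in situ repair, the crude percentages with persistent pain will be accompanied by a Mantel-Haenszel risk difference or risk ratio stratified by hospital, with a 95% confidence interval. Counts of Yes, No and not found will be tabulated per hospital, and the number of hospitals contributing both techniques will be stated. Records with technique not found will be reported as a separate group and will not be merged with No in the main comparison. If the stratified estimate is uninformative, the crude result will be described as unadjusted and not as an effect of technique.*

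The per-hospital table also tests the assumption on which the point rests: if technique use is similar across hospitals, crude and stratified figures should nearly agree.

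The cost is in wording and analysis only. Hospital should be identifiable without new data collection, since Data collection and Data Protection Authority describe a data manager at each hospital. The downside is a wider interval: single-technique hospitals contribute nothing, and the expected 21 to 95 cases may leave the stratified estimate inconclusive.

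### Renewed opt-in after 12 months can shift the 2- to 5-year pain percentages, and reporting only the amount of missing data would not reveal it

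*Protocol*

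**What the plan says.** **Consent.** Under Informed consent, the 30-day questionnaire covers only the first year: "patients are asked if they wish to continue participating in the survey with questionnaires at 5 weeks, 2, 3, 6, and 12 months". Beyond that, agreement is renewed (the quoted sentence breaks off before its last word): "In the questionnaires after 12 months, 2, 3, and 4 years, the patients are once again asked about their willingness to continue participating in the". For those who agree, the section adds: "If they consent, a new consent statement is sent to them annually".

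**Outcomes.** Exploratory outcome 2 is worded as follows, with the last four times in years: "Percentage of patients experiencing pain with an NRS > 3 at 1, 2, 3, and 12 months, as well as 2, 3, 4, and 5". Exploratory outcomes 5 and 6 relate persistent pain to pre-pregnancy chronic pain and to uterine exteriorization, again out to 5 years. The secondary outcomes are also assessed every 6 months after the first year.

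**Analysis.** Data Processing and statistics plans descriptive summaries, with frequency and percentage for categorical data. On losses it mentions direct SMS delivery and reminders, and then: "The amount of missing data will be accounted for when describing data". On timing: "We analyze the data when the last of the included patients have completed the 12-month questionnaire and again after every year". The section does not define the denominator at each round and does not mention comparing those who continue with those who stop.

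**Size.** The sample is one of convenience, "with an expected participation rate of approximately half of the 700 patients from the initial cohort study agreeing to continue". Number of participants adds: "We aim to include at least 300 patients from all 5 regions in Denmark". No continuation rate after 12 months is given.

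**The concern.** The Objective is to describe pain over months and years. A reader will take a row of percentages at 12 months and at 2, 3, 4 and 5 years as a course over time. After 12 months, each figure comes from a group that has chosen once more to go on answering questions about pain.

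That choice could plausibly depend on pain in either direction. Someone free of pain may see little reason to continue, and someone with pain may tire of the survey. If it does depend on pain, the percentage moves although nobody's pain has changed. Reminders deal with unanswered questionnaires, not with a declined consent.

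The stated handling reports how many are missing, which is the one feature of the loss that carries no information about direction. Yet participants who stop will generally have earlier NRS reports in the same REDCap database, so the loss can be examined without collecting anything new.

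**Working it through.** **The plan's own figure.** Half of 700 is 700 × 0.5 = 350. This agrees with the minimum of 300, which is 300/700 = 42.9%. No power or precision figure is stated, so there is nothing further to reproduce.

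**Inputs**
- From the protocol: four renewal points (12 months, 2, 3 and 4 years) before the 5-year figure, and about 350 participants.
- Assumed: true prevalence of NRS > 3 at 12 months p = 10%; nobody's pain status changes afterwards; all 350 still present at 12 months; continuation probability a per point with pain and b without.

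**Formula.** After k renewal points, the observed percentage is p·a^k / [p·a^k + (1 − p)·b^k].

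**10-point difference, k = 4** (0.9^4 = 0.6561; 0.8^4 = 0.4096)
- a = 0.9, b = 0.8: 0.06561 / (0.06561 + 0.36864) = 15.1%. Remaining: 350 × 0.43425 ≈ 152.
- a = 0.8, b = 0.9: 0.04096 / (0.04096 + 0.59049) = 6.5%. Remaining: 350 × 0.63145 ≈ 221.

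| a / b | 12 months | 2 y | 3 y | 4 y | 5 y |
|---|---|---|---|---|---|
| 0.9 / 0.8 | 10.0 | 11.1 | 12.3 | 13.7 | 15.1 |
| 0.8 / 0.9 | 10.0 | 9.0 | 8.1 | 7.2 | 6.5 |

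**20-point difference, k = 4** (0.7^4 = 0.2401)
- a = 0.9, b = 0.7: 0.06561 / (0.06561 + 0.21609) = 23.3%.
- a = 0.7, b = 0.9: 0.02401 / (0.02401 + 0.59049) = 3.9%.

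**Other prevalences.** The rates cited in the Background serve here only as scenario values. With 90% against 80% either way, an unchanged 5.9% becomes 9.1% or 3.8%; 11% becomes 16.5% or 7.2%; 27% becomes 37.2% or 18.8%.

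**Continuation unrelated to pain.** If a = b the percentage does not move. At 80% per point, 350 × 0.4096 ≈ 143 remain, and only precision suffers.

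**What a tabulation by continuation status would show.** In the 0.9 / 0.8 case, the 5-year continuers also had 15.1% at 12 months, because nobody changed. Those who stopped had 0.10 × (1 − 0.6561) = 0.03439 with pain out of 0.03439 + 0.90 × (1 − 0.4096) = 0.56575, which is 6.1%. In the 0.8 / 0.9 case, those who stopped had 0.05904 / 0.36855 = 16.0%. Setting 15.1% against 6.1%, or 6.5% against 16.0%, exposes the drift at once. The amount missing does not.

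**Odds ratios.** If continuation depends on pain alone, the odds of pain are multiplied by (a/b)^4 in each exposure group; for 0.9 / 0.8 this is 1.125^4 = 1.60. The factor is the same in both groups and cancels from the odds ratio.

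**The case against.** The strongest objection is that this is silence rather than error. Weighting, repeated-measures models and tables of continuers against leavers commonly belong in an SAP, which may exist. The sentence on missing data is not false and excludes none of them. That has force: the absence of a named model alone would not be a finding. What remains is that the protocol does state a handling rule, covering quantity only, alongside a consent design that re-selects the respondents four times.

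Several stronger readings are tempting and are not supported:
- *The plan formally compares years.* It lists percentages at time points and plans no test of trend. The issue is how a descriptive series will be read.
- *The main result is at risk.* The primary outcome at 6 months precedes any renewal. The 12-month figure is also unaffected, because the first renewal question sits in that questionnaire. Exploratory outcome 3 ends at 12 months.
- *The associations in exploratory outcomes 5 and 6 are biased in the same way.* Selection on pain alone cancels from an odds ratio. Bias there needs continuation to depend jointly on exposure and pain. Risk differences would shift, but no effect measure is named.
- *Patients decide straight after scoring their pain, and no reason for stopping is recorded.* The order of items is not given, and the question overview in Appendix 8 is not shown.

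It is also fair to say that annual renewal is part of a consent procedure that the protocol describes as approved. It is not itself a fault.

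**Conclusion.** The point holds for the 2- to 5-year percentages in exploratory outcome 2 and for secondary assessments after 12 months. The stated handling cannot separate a change in pain from a change in who answers.

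Drift is possible, not certain: it requires continuation to depend on pain, and the documents give neither its direction nor any continuation rate. With a true 10% held constant, an assumed 10-point difference at every renewal gives 15.1% or 6.5% at 5 years. A reader might infer that a flat course could appear more than doubled or less than halved. At this prevalence that takes an assumed 20-point difference, in the same direction, at all four points (23.3% or 3.9%), and nothing in the protocol supports a gap of that size. The change is worth making for the late series, and it does not call the primary result into question.

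**What to change.** In Data Processing and statistics, add for rounds after 12 months:

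1. Beside each year's percentage with NRS > 3, report the 6- and 12-month percentages in the same continuing patients and, separately, in those who have stopped.
2. As a sensitivity analysis beside the raw series, estimate the prevalence of NRS > 3 over time. Use either a repeated-measures model with all rounds from all participants, or weights equal to the inverse probability of continuing given the last NRS, pre-pregnancy chronic pain and severe acute pain.

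Step 1 is tabulation of data already held. Step 2 is modest extra analysis. Its adjusted figure assumes that earlier reports explain continuation, so it should stand next to the raw figure and not replace it.

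An optional tick-box for the reason for stopping, if none exists already, would be a useful extra but is not essential. It would have to be in the questionnaire before the renewal point that it is meant to cover.

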## Outcomes

All outcomes related to **pain**, refer to pain in or around the surgical area. Assessments are conducted at 5 weeks, 2, 3, 6, and 12 months, and after that every 6 months until 3 years after surgery.

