### *Primary outcome*

The percentage of patients reporting pain equivalent to an NRS score > 3 after 6 months

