### *Secondary outcomes*

1. Severe pain during the last 24 hours. NRS 0-10
2. Pain at rest during the last 24 hours. NRS 0-10
3. Use of analgesic medication in the past week due to pain (Paracetamol, Non-Steroidal Anti-Inflammatory Drug, opioid). Yes/No. What kind.
4. Pain's affect on daily activities. 1-5: Not at all, a little, to some extent, to a great extent, cannot do due to pain.
5. Pain's affect on engaging in strenuous physical activity. 1-6: Not at all, a little, to some extent, to a great extent, cannot do due to pain, I don't know - I haven't tried.
6. Pain's affect on meeting the infant's needs. 1-5: Not at all, a little, to some extent, to a great extent, cannot do due to pain.
7. Pain's affect on sleep. 1-4: Not at all, a little, to some extent, to a great extent.
8. Pain's affect on mood. 1-4: Not at all, a little, to some extent, to a great extent.
9. Pain/discomfort when sitting down or standing up from a chair. 1-5: Not at all, a little, to some extent, to a great extent, cannot do due to pain.
10. Pain/discomfort when walking on stairs. 1-5: Not at all, a little, to some extent, to a great extent, cannot do due to pain.

11. Pain/discomfort when getting in or out of bed. 1-5: Not at all, a little, to some extent, to a great extent, cannot do due to pain.
12. Pain/discomfort when carrying the infant. 1-5: Not at all, a little, to some extent, to a great extent, cannot do due to pain.
13. Pain/discomfort when sitting up for less than 30 minutes. 1-5: Not at all, a little, to some extent, to a great extent, cannot do due to pain.
14. Pain/discomfort if sitting up for more than 30 minutes. 1-6: Not at all, a little, to some extent, to a great extent, cannot do due to pain, I don't know - I haven't tried.
15. Pain/discomfort when moving around at home. 1-5: Not at all, a little, to some extent, to a great extent, cannot do due to pain.
16. Pain/discomfort if walking for more than 30 minutes. 1-6: Not at all, a little, to some extent, to a great extent, cannot do due to pain, I don't know - I haven't tried.
17. Pain/discomfort when bending down. 1-5: Not at all, a little, to some extent, to a great extent, cannot do due to pain.
18. Pain/discomfort during or after sexual intercourse. 1-7: Not at all, a little, to some extent, to a great extent, cannot do due to pain, I don't know - I haven't tried, I prefer not to answer.

Neuropathic pain (Andersen et al. 2019):

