## Data collection

The questionnaires are sent at fixed time intervals: at 5 weeks, 2 months, 3 months, 6 months, and 12 months, and thereafter every 6 months until 5 years after CD. Reminders are sent the day after the initial questionnaire in case of no response. All questionnaire data are entered directly into the closed and secure system REDCap. Data from journal entries are also entered into REDCap. At all hospitals, a data manager can retrieve data for the patients included in the project. The primary investigator holds the overall responsibility for the data.

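### The primary percentage has no stated denominator, and missing 6-month answers are only counted, so a modest bias from pain-related non-response would go unexamined

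*Protocol*

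**What the plan says.** The Primary outcome section defines one proportion: "The percentage of patients reporting pain equivalent to an NRS score > 3 after 6 months". It does not say of whom: all who consented, or those who answered that round.

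Data Processing and statistics makes three relevant statements. The analysis type is "Descriptive statistics will be used to analyze data", with categorical data given as frequency and percentage. Prevention of missing data is "We will try to minimize missing data as much as possible by sending questionnaires directly to the participants mobile phones and sending reminders"; Data collection adds "Reminders are sent the day after the initial questionnaire in case of no response". The treatment of what is still missing at analysis is "The amount of missing data will be accounted for when describing data".

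Other rounds surround the primary one: "Assessments are conducted at 5 weeks, 2, 3, 6, and 12 months". NRS pain items such as "Pain at rest during the last 24 hours. NRS 0-10" are listed as outcomes, and the Outcomes section schedules assessments at each of these rounds. The 3-month and 12-month answers also serve as outcomes in their own right ("Percentage of patients experiencing pain with an NRS > 3 at 1, 2, 3, and 12 months"). The first analysis waits for the last participant's 12-month questionnaire. Any NRS given on either side of 6 months will therefore be in the database when the primary result is computed.

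**The concern.** The study exists to estimate how often persistent pain occurs, and its primary result is one proportion without a comparison group. In a contrast between groups, similar non-response on both sides may partly cancel. Here nothing cancels.

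Women without pain may find a pain questionnaire irrelevant and skip it, which raises the responders' percentage. Women burdened by pain may skip it, which lowers it. The protocol cannot tell which will dominate. Reporting the number missing tells a reader that the problem may exist, but not its direction or size. Some participants who skip 6 months may have answered at other rounds, and the plan as written makes no use of those answers for the primary result.

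**Working it through.** **Inputs from the protocol.** The expected size is half of 700: 700 × 0.5 = 350, which agrees with the stated aim of at least 300. There is no power calculation to reproduce. Background gives 5.9% (daily or almost daily scar pain) and 11–27% (any pain at six months). Neither is NRS > 3.

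**Assumptions, none of them in the protocol.** True prevalence is 8% at each round. Correlation within a woman on a latent normal scale is 0.7. Response is 85% at 3 months and 75% at 12 months. Under this model 3.53% of women have pain at both 3 and 6 months, and 8 − 3.53 = 4.47% have it at 6 months but not at 3.

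**Responders' percentage, by what drives 6-month response**

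- *A. Response 90% after pain at 3 months, 65% after none.* Overall response is 0.08 × 0.90 + 0.92 × 0.65 = 0.670, or about 235 women. Percentage: (0.0353 × 0.90 + 0.0447 × 0.65) / 0.670 = 9.1%, an error of +1.1 points.
- *B. Response 65% after pain at 3 months, 85% after none.* Overall response is 0.08 × 0.65 + 0.92 × 0.85 = 0.834, or about 292 women. Percentage: (0.0353 × 0.65 + 0.0447 × 0.85) / 0.834 = 7.3%, an error of −0.7 points.
- *C. Response 90% with pain at 6 months, 65% without.* Percentage: 0.08 × 0.90 / 0.670 = 10.7%. Simulation at n = 350 averages 10.8%, an error of about +2.8 points.

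**Same scenarios with all 350 as denominator.** Non-responders then count as pain-free: A gives 9.1% × 0.670 = 6.1%, B gives 7.3% × 0.834 = 6.1%, and C gives 7.2%. All lie below 8%. Even 80% response unrelated to pain would give 8% × 0.80 = 6.4%.

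**Sampling error for scale.** 1.96 × √(0.08 × 0.92 / n) is 3.2 points at n = 280, 3.5 at n = 235 and 3.1 at n = 292.

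**What the other rounds recover.** Filling the missing 6-month status from the 3-month and 12-month answers moves A from 9.1% to 8.1%, B from 7.3% to 7.9%, and C from 10.8% to 10.2%. The bias in A and B is largely removed; in C only a small part is.

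**Sensitivity range, illustrated.** Take 280 responders of 350, 22 with pain (7.9%), and 70 non-responders imputed at the same odds, 22/258 = 0.0853.

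- Half the odds: 0.0426 / 1.0426 = 4.1%, so (22 + 70 × 0.041) / 350 = 7.1%.
- Twice the odds: 0.1705 / 1.1705 = 14.6%, so (22 + 70 × 0.146) / 350 = 9.2%.
- Extreme bounds: 22/350 = 6.3% and (22 + 70)/350 = 26.3%.

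**The case against.** The strongest objection is that imputation methods usually belong in a statistical analysis plan, which is not shown here, and that counting the missing is a transparent choice for a descriptive convenience cohort. This carries weight against any claim that a method is absent. But the protocol is not silent: it fixes a descriptive percentage and one treatment of missing answers, and it leaves the denominator open. A better method is available at little cost with data already planned.

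Two stronger readings are tempting and not supported. A reader might infer that the protocol prescribes a responders-only analysis. It does not; that is the natural reading of an unstated denominator. A reader might also infer that most women who skip 6 months will have an NRS at 3 or 12 months. The protocol gives no response rate for any round, and a woman who has stopped answering has no 12-month value. If 20% of skippers answer each adjacent round, only 20% (the same women) to 1 − 0.8² = 36% (independently) have either value. All that can be said is that some may.

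The recovery figures above also assume that answering one round is independent of answering another. With response correlated within women (latent 0.7, also assumed), the same simple fill gives only 8.8% in A and 7.6% in B, and in C it moves further from the truth, to 12.2%. That loss comes from the crude fill. A likelihood analysis assuming missing at random, which multiple imputation approximates, still gives 8.2%, 7.9% and 10.2%.

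The objection on size stands. The error that imputation removes is about 1 point or less, well inside the sampling error, and the extreme bounds describe a worst case that imputation does not narrow.

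**Conclusion.** The point holds in a limited form. The protocol names no denominator for its primary percentage and states only that the amount of missing data will be accounted for. Either plausible denominator gives a biased figure when response depends on pain.

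Under the assumptions stated, the responders' figure errs by about 0.7 to 1.1 points when response follows pain at 3 months, and by about 2.8 points when it follows pain at 6 months. Both are below the half-width of about 3.2 to 3.5 points. Unlike sampling error, however, this error does not shrink with more participants, and a confidence interval does not show it. This is a worthwhile improvement, not a flaw that invalidates the study. The direction and true size cannot be known from the protocol.

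**What to change.** In Data Processing and statistics:

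1. Name women who answered at 6 months as the denominator of the observed primary percentage. Keep it as the main result, with the number missing beside it.
2. Add a sensitivity estimate for all enrolled women by multiple imputation of the 6-month NRS from the NRS at 5 weeks, 2, 3 and 12 months, analgesic use and acute NRS, for women who gave those answers.
3. Add a range in which the odds of pain among non-responders are half and twice the imputed odds.

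The cost is a few lines of text and a little analysis work, with no new data collection. The imputation assumes missing at random and corrects only part of the bias if response depends on 6-month pain itself. The range is there for that case, but it is not a bound. In scenario C the imputed 10.2% implies (10.2 − 7.2)/0.33 = 9.1% among non-responders. Halving those odds gives 4.8%, and 7.2 + 0.33 × 4.8 = 8.8% overall, which covers most of the gap to 8% but not all of it.
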